23.1 Compensation for Injury

If a subject suffers any health damage due to participation in this study, the sponsor will appropriately compensate according to the standard specified by the sponsor unless the causal relationship with the study is denied (Compensation consists of medical expenses < copayment portion >, medical allowance, and compensation payment.). In this case, the subject shall not bear the burden of proof of causal relationship, etc.

23.2 Insurance

The sponsor will take necessary measures, such as purchasing insurance, to ensure the fulfillment of the liability for compensation and indemnification for study-related health injury in subjects.

24. Publications

The information contained in this protocol is the property of the sponsor and will be provided to the persons involved in the study such as the investigator (subinvestigator) who conduct this study and the institutional review board, but must not be disclosed to any third party without written agreement of the sponsor except when it is necessary for the conduct of the study.

If persons involved in the study at the study site such as the investigator (subinvestigator) publish information obtained from the study externally such as to a professional academic conference, prior approval of the sponsor must be obtained.

The sponsor is free to use the information obtained from this study for the purpose of reporting to the regulatory authorities, proper use of drugs, marketing, etc.

25. Gene analysis test

For sites where blood samples for the genetic analysis study can be collected, specific procedures will be followed and the genetic analysis study will be performed as specified in this section.

25.1 Objectives

Obtaining knowledge of drug effects and the relationship between adverse events and genes is important in establishing safer and more pharmacodynamically evaluated therapies. In the future, genetic analysis may also be performed for MCI-186 in order to investigate individual differences in drug response related to effects and adverse events. Therefore, blood samples will be collected and DNA extract samples will be stored in this study.

25.2 Study Population

Subjects who consent to participate in this study and the genetic analysis study will be included.

25.3 Informed Consent

In cooperation with the sponsor, the investigator will prepare the informed consent form for the gene analysis study separately from the informed consent form for participation in the study itself.

The prepared and revised documents should be submitted to the sponsor and approved by the IRB.

Prior to blood sampling for the gene analysis study, the Investigator (or Subinvestigator) will provide subjects with the informed consent form for the gene analysis study, provide them with a full explanation of the study, and obtain their written voluntary consent to participate in the gene analysis study.

The investigator (subinvestigator) who explained the study and the subject will sign (or mark with a seal) and date the informed consent form, and provide the subject with a copy of the completed form. If a study collaborator has provided supplementary explanation, the study collaborator will also sign (or mark with a seal) and date the informed consent form.

Even if consent for the genetic analysis study is not obtained, participation/continuation in the study is allowed if consent for the study is obtained.

25.4 Handling of samples

The blood samples will be stored at a contract research organization for storage of blood samples for genetic analysis.

25.4.1 Date of blood collection

Approximately 8.5 mL of whole blood will be collected into a blood collection tube containing an anticoagulant once at any time point from the start of investigational product to the evaluation day 3 months after the onset.

25.4.2 Storage and Shipping Conditions

Blood samples will be stored frozen until shipment. Blood samples will be collected by the contract clinical laboratory and sent to the genetic analysis sample storage facility. The contract clinical laboratory will store the collected blood samples in a frozen state until they are sent to the genetic analysis sample storage facility, and send them on sufficient dry

ice. The genetic analysis sample storage facility will extract DNA from the transported blood samples and store the DNA extract collectively in the genetic sample storage cabinet.

25.4.3 Procedures for anonymization/coding, preparation and storage of correspondence table

The genetic analysis sample storage facility will anonymize the transported blood samples in a linkable fashion, assign a sample anonymization number different from the subject number, and store the correspondence table. For details such as the method of anonymization and preparation/storage of the correspondence table, follow the written procedures of the genetic analysis sample storage facility or the study protocol.

25.4.4 Sending a copy of the correspondence table

A copy of the correspondence table prepared by the genetic analysis sample storage facility will be sent to the sponsor after completion of storage of the final sample.

25.4.5 Storage Period of DNA Extract Samples

The DNA extract samples will be stored for no longer than 15 years after completion of the study.

25.4.6 Disposal of Blood and DNA Extract Samples

The blood residue after DNA extraction will be discarded according to the written procedures of the genetic analysis sample storage facility or the study protocol.

In principle, the DNA extract samples will be stored for the period specified in 25.4.5 after the completion of the study, and then will be disposed of by the genetic analysis sample storage facility according to the written procedures prepared after obtaining the confirmation of the sponsor's consent to disposal.

If a subject withdraws his/her consent for the genetic analysis study, his/her DNA extract sample or blood sample will be discarded immediately after anonymization of samples.

25.5 Implementation of genetic analysis

Samples obtained for the genetic analysis studies will only be used for pharmacodynamic assessment of MCI-186 and genetic analysis related to safety drug response. Genetic analysis will be performed when the sponsor judges it necessary to examine regardless of the duration of this study, and it may not be performed. If a study using these samples is to be started, a protocol containing the contents of the study will be newly prepared, and the report will be prepared separately from the clinical study report of this study.

25.6 Publication of Analysis Results and Disclosure to Subjects Who Provided Samples

25.6.1 Publication of Analysis Results and Disclosure to Subjects Who Provided Samples

If persons involved in the study at the study site such as the investigator (subinvestigator) publish information obtained from the gene analysis study externally such as to a professional academic conference, prior approval of the sponsor must be obtained. The sponsor may freely use the information obtained from the analysis for the purpose of reporting to the regulatory authorities, proper use of drugs, marketing, etc.

In principle, genetic information obtained from analyses in individual subjects who provide specimens will not be disclosed to the donors themselves when the evaluation has not been established (clinical significance is unclear).

1. INTRODUCTION

This statistical analysis plan (SAP) is based on the final protocol version 01.01 dated 1 August 2017. The plan covers statistical analysis, tabulations and listings of efficacy and safety data to investigate the efficacy and safety of MCI-186 (bolus followed by 72-hour continuous infusion) in acute ischemic stroke patients through a double-blind, parallel-group comparison with the existing MCI-186 dosing regimen as the control.

The SAP is prepared by Mitsubishi Tanabe Pharma Corporation(MTPC), Data Science Department. The statistical analyses and production of the outputs described in the SAP will be conducted and QC checked by [REDACTED] Medical Development Business Department2 SAS Consulting Group, using SAS® 9.3 or later Software. The final analyses and outputs will be approved by Mitsubishi Tanabe Pharma Corporation, Data Science Department.

MTPC has early decided to stop subjects's recruitment based on internal decision. Therefore, the planned sample size will not be completed so that this plan will be executed based on a limited available sample size. The finding for this statistical analysis will lead to exploratory results.

2. STUDY OBJECTIVE(S) AND ENDPOINTS

2.1 Study Objective(s)

To investigate the efficacy and safety of MCI-186 (bolus followed by 72-hour continuous infusion) in acute ischemic stroke patients through a double-blind, parallel-group comparison with the existing MCI-186 dosing regimen as the control.

2.2 Primary Efficacy/Safety Endpoint(s)/Assessments

- Primary endpoint

NIHSS (change over the 7 days from onset)

2.3 Secondary Efficacy/Safety Endpoint(s)/Assessments

- Secondary endpoints

- (1) NIHSS (Day 4, Day 7, Day 10, Day 14, after 3 weeks, at discharge, after 3 months)
- (2) mRS (after 3 weeks, at discharge, after 3 months)
- (3) BI (Day 14, after 3 weeks, at discharge, after 3 months)
- (4) FIM (after 3 weeks, at discharge, after 3 months)
- (5) Start of rehabilitation

- (6) Duration of hospitalization
- (7) Cranial imaging diagnosis

2.4 Safety Assessment(s)

- Safety endpoints
 - (1) Adverse events and adverse reactions
 - (2) Neurological testsassessments
 - (3) Common clinical laboratory tests
 - (4) Vital signs
 - (5) Standard 12-lead ECG

2.5 Pharmacokinetics Endpoint(s)/Evaluation(s)

Not applicable in the study.

2.6 Pharmacodynamics Endpoint(s)/Evaluation(s)

Not applicable in the study.

2.7 Other Endpoint(s)/Evaluation(s)

- Exploratory endpoint

[figure not shown]
3. STUDY DESIGN

3.1 Study Design

Phase of study : Phase 2

Study type : Confirmatory study (planned)

Multicenter, randomized, double-blind, parallel-group study with the approved dosing regimen as the control

Rationale

This study was designed as a parallel-group comparative study with the existing dosing regimen as the control in order to objectively investigate the efficacy and safety of the 72-hour continuous infusion dosing regimen. In addition, in order to minimize rater bias, a double-dummy method will be used to administer the investigational product, and the study will be conducted using a randomized, double-blind method.

3.2 Schedule of Study Procedures

Study assessments are summarized in the Time and events schedule (Table 1).

Table 1: Assessment and Observation Schedule

Assessment Time Point	Before Treatment Initiation		Study Drug Treatment Period							Observation period					
	Consent	Confirmation of suitability	Registration	Day 1	Day 2	Day 3	Day 4	Day 5	Day 7	Day 10	Day 14 or study drug treatment period discontinuation ^a	After 3 weeks ^b	At discharge	After 3 months ^c or at observation period discontinuation	
Allowable Range										± 1 day	± 1 day	+1 day	± 2 days	-1 day	± 8 days (+8 days)
Consent acquisition	●														
Subject background		●													
Registration/allocation			●												
Study drug treatment				72-hour continuous infusion							Twice a day for 14 days ^d				
NIHSS		●		Assessments performed every day for 7 days after treatment initiation							●	●	●	●	●
mRS ^e		● ^f										●	●	●	●
BI												●	●	●	●
FIM												●	●	●	●
Diagnostic imaging		DWI T2*WI FLAIR MRA					DWI ^g T2*WI ^g				DWI T2*WI				FLAIR
Neurological assessments				● ^h							●	●	●	●	●
Standard 12-lead ECG	●						● ⁱ								
Vital signs	●						● ⁱ		●		●				
Clinical laboratory tests (centralized measurements)	●						● ⁱ		●		●		●	●	
Clinical laboratory tests (site measurements)		● ^j		Measured every day for 5 days after treatment initiation ^k											
PGx blood sample collection				● (Blood samples will be collected during the study from subjects who have consented to having blood samples collected for genetic analysis)											
Adverse events															
Concomitant medications															

- a) If the study is discontinued during the study drug treatment period, the tests that are stipulated should be conducted at study drug treatment period discontinuation will be conducted, and whenever possible subject safety will be evaluated at 3 months after onset.
- b) In this study, "after 3 weeks" is defined at Day 22. If a subject is discharged within 3 weeks after treatment initiation, then the tests that are stipulated should be performed at discharge will be performed, and the tests that are scheduled for after 3 weeks will not be necessary.
- c) In this study, after 3 months is defined as Day 85. If the study is going to be discontinued during the observation period, then the tests that are stipulated should be conducted at observation period discontinuation will be conducted, and subject safety will be assessed after 3 months whenever possible.
- d) Twice a day, at morning and at night, for 14 days. As a rule, the drug is administered for 14 days. However, in the period after the treatment has been administered for 7 days following treatment initiation and the NIHSS assessments have been completed, treatment may be stopped only if the (sub)investigator determines that the neurological symptoms associated with the primary disease have returned to their baseline levels, the patient's condition has stabilized, and that consequently continuing to administer the study drug would not be clinically meaningful, and administering the drug would only be detrimental for the subject in that it would restrict the

subject's freedom. (the subject may not be discharged).

- e) The mRS assessments will be performed using the Japanese-language version of the mRS questionnaire (Cerebrovasc Dis 2006;21:271-278) (Attachment 2: mRS Questionnaire; Attachment 3: mRS Assessment Criteria).
- f) The mRS assessment will also be performed prior to treatment initiation.
- g) Imaging will be performed after the end of the 72-hour continuous infusion (+ 2 days).
- h) The neurological assessments will be performed once in the period between the time of consent acquisition and Day 5.
- i) The standard 12-lead ECG, vital signs, and clinical laboratory tests (centralized measurements) will be performed before the end of the 72-hour continuous infusion (-1 day).
- j) The following tests will be conducted urgently at the hospital to confirm the patient's eligibility: WBC, RBC, hematocrit, hemoglobin, platelets, AST (GOT), ALT (GPT), LDH, ALP, γ -GTP, total bilirubin (T-Bil), CK (CPK), urea nitrogen (BUN), serum creatinine (Cre), and eGFR.
- k) The red blood cell (RBC), platelet (Plt), AST (GOT), ALT (GPT), LDH, ALP, total bilirubin (T-Bil), CK (CPK), urea nitrogen (BUN), and serum creatinine (Cre) levels only will be performed at the site every day from the day after treatment initiation through Day 5 after treatment initiation to confirm subject safety.

3.3 Sample Size and Power Considerations

- A total of 336 subjects as randomized subjects
 - Group H: 120 subjects
 - Group L: 96 subjects
 - Control group: 120 subjects

Rationale

4. PLANNED ANALYSES

4.1 Data Monitoring Board (DSMB)

No DSMB will be performed for this study.

4.2 Interim Analysis

No interim analysis will be performed for this study.

4.3 Final Analysis

All final, planned analyses identified in this SAP will be performed by MTPC Authorization of this Statistical Analysis Plan, Database Lock, Authorization of Analysis Populations and Unblinding of Treatment.

Final analysis will be done after database lock as per this SAP.

The final database lock will occur when all outstanding data queries have been resolved and the database is fully cleaned. These data will then be used to produce a full set of unblinded tables, figures and listings planned in this SAP for the Clinical Study Report. The tables, figures and listings will then be communicated to the wider study team.

6. GENERAL CONSIDERATIONS

Efficacy endpoints will be analysed on the FAS population and listed on the FAS population. Subjects will be analysed according to the treatment group they were randomised to. Safety analyses will be performed on the SAF. Subjects will be analysed according to the treatment group they were actually received.

In general, continuous variables will be summarized descriptively using the number of observations (n), mean, standard deviation (SD), median, minimum and maximum. Categorical variables will be summarized using frequency counts and percentages. The denominator for the percentages will be the total number of subjects in the relevant group and population (analysis set) being presented, unless otherwise specified (e.g., on some occasions, percentages maybe calculated out of the total number of subjects with available data at a particular visit and/or time point).

For each section, baseline is the last valid assessment prior to the start of IMP administration. For numerical variables, change from baseline will be calculated as the post-baseline value minus the baseline value. If baseline value cannot be determined for a particular variable, change from baseline will not be calculated.

Data will be handled as follows.

(1) Definition of missing data

When test values are missing, or could not be measured because of, for example, a problem with the test sample, these values will be handled as missing. In addition, no imputation will be made in case of missing values.

(2) Handling of the data at measurement time points

When summarizing the data at each measurement time point, data within the analysis time windows defined in Appendix 1 will be used. If multiple values were obtained within the time window, then the value closest to the planned assessment day will be used.

Unscheduled visits will not be displayed in by-visit summary tables, but will be included in the data listings.

Listings will include scheduled, unscheduled, retest and early discontinuation data.

The date and times of start and end of IMP administration will be taken from the Electronic Case Report Form (eCRF) Dosing form.

All medical history and adverse events will be coded from the actual term using the Medical Dictionary for Regulatory Activities (MedDRA) version 20.0.

All prior and concomitant medications will be coded using the World Health Organization (WHO) drug dictionary (Version: WHO DDE B2 Mar_2017).

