The investigator (subinvestigator) will measure all of the following tests at the contract laboratory testing institution on Day4 (before the end of continuous intravenous infusion), Day7, Day10, Day14, Week 3, and at discharge, and record the date of confirmation of test results and the results of confirmation (clinical significance). The test results provided by the contract laboratory testing institution will be retained by the study site and the sponsor.

The test items are as follows.

- Hematology: white blood cell count (WBC), red blood cell count (RBC), hematocrit (Ht),
Hemoglobin (Hb), Platelets (Plt)
- Blood biochemistry: AST (GOT), ALT (GPT), LDH, ALP, γ -GTP,
Total bilirubin (T-Bil), direct bilirubin (D-Bil),
Total cholesterol (T-Chol), triglycerides (TG), total protein (TP),
CK (CPK), Blood urea nitrogen (BUN), Serum creatinine (Cre), eGFR,
Uric acid (UA), Na, K, Cl, albumin, glucose
- Urinalysis (qualitative): Sugar, protein, occult blood

(2) Standard 12 lead ECG

The investigator (subinvestigator) will perform standard 12 lead ECG at baseline and Day4 (before completion of continuous intravenous infusion) to determine whether there are any abnormal findings. The date and time of standard 12 lead ECG, ECG parameters (Heart rate, PR interval, QRS interval, RR interval, QT interval, and QTc interval), and assessment results will be recorded in the CRF. Clinically significant abnormal findings, if determined by the investigator or subinvestigator, should be recorded as adverse events. The investigator will maintain ECG charts as source documents.

(3) Vital signs

The investigator/subinvestigator will measure systolic/diastolic blood pressure, pulse rate, and body temperature (Axillary, oral or tympanic body temperature) before administration, on Day4 (before the end of continuous intravenous infusion), Day7, and Day14, and record the date of measurement and the test results in the case report form. Blood pressure should be measured in the same arm throughout the study period whenever possible. Clinically significant abnormal findings, if determined by the investigator or subinvestigator, should be recorded as adverse events.

(4) Neurological Examination

The Investigator (or Subinvestigator) will perform a neurological examination on the healthy side once from the onset to Day5, and then on Day14, Week 3, at the time of discharge, and 3 months later. The tests that may be

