7.3.2 Laboratory Tests

Laboratory parameter values and changes from baseline, except for urinalysis will be summarized descriptively by analysis visit.

Clinical significance of laboratory findings will be evaluated by the Investigator with respect to pre-defined clinically relevant ranges taking into account the Investigator site's normal ranges. The laboratory data will be listed in full with clinically relevant values flagged (L=Lower than normal range, H=Higher than normal range or A=Abnormal if no reference range). A listing of laboratory values will be provided for subjects with any clinical significant findings (list relevant laboratory parameters only).

Lab parameter values and changes from baseline will be summarized descriptively by treatment group and analysis visit.

Shift tables will present the changes in clinically relevant categories from baseline to each analysis visit. The categories will be qualitative values for Urinalysis.

The test parameters(from central laboratory) are listed below.

- * Hematology tests: White blood cell count (WBC), red blood cell count (RBC), hematocrit (Ht), hemoglobin (Hb), platelets (Plt)
- * Blood biochemistry tests: AST (GOT), ALT (GPT), LDH, ALP, γ -GTP, total bilirubin (T-Bil), direct bilirubin (D-Bil), total cholesterol (T-Cho), triglycerides (TG), total protein (TP), CK (CPK), blood urea nitrogen (BUN), serum creatinine (Cre), eGFR, uric acid (UA), Na, K, Cl, albumin, glucose
- * Urinalysis (qualitative): Glucose, protein, occult blood

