7.3.3 Vital Signs

All vital sign data will be listed.

Vital signs (systolic blood pressure, diastolic blood pressure, pulse rate, body temperature) values and changes from baseline will be summarized descriptively by analysis visit.

7.3.4 12-lead ECG

All 12-lead ECG (heart rate, RR, PR, QRS, QT, QTcF, overall evaluation) parameters and findings will be listed.

12-lead ECG parameter values and changes from baseline will be summarized descriptively by analysis visit.

For ECGs, number and percentage of subjects meeting the criteria listed below will be presented:

- $QTcF > 500$ msec at timepoint
- $500 \geq QTcF > 480$ msec at time point
- $480 \geq QTcF > 450$ msec at time point
- Change from baseline in $QTcF > 30$ msec
- Change from baseline in $QTcF > 60$ msec

Number of normal or abnormal values will be summarized by analysis visit window.

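### No by-arm summary table captures the worst post-baseline laboratory or ECG value, so shift and QTcF counts can understate threshold crossings

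*SAP*

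**What the plan says.** Two selection rules stand in SAP section 6. The first is "Unscheduled visits will not be displayed in by-visit summary tables"; such values go to the listings instead. The second is "If multiple values were obtained within the time window, then the value closest to the planned assessment day will be used". The windows are in SAP Appendix 1. The same section promises full detail elsewhere: "Listings will include scheduled, unscheduled, retest and early discontinuation data".

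The safety sections build on these rules:

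- **Laboratory (SAP 7.3.2).** Values and changes are summarised by treatment group and analysis visit. For categories, "Shift tables will present the changes in clinically relevant categories from baseline to each analysis visit".
- **ECG (SAP 7.3.4).** Parameters are summarised by analysis visit. Then "For ECGs, number and percentage of subjects meeting the criteria listed below will be presented". The three absolute QTcF bands are tied to a time point; the rows for a change above 30 or 60 msec give no time rule.
- **Outputs (SAP 14.2).** The laboratory shift tables are 14.3.2.4 to 14.3.2.6 and the QTcF table is 14.3.4.2. No table is described as worst, maximum or any-time post-baseline.

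Protocol 9.2.4.1 schedules one post-dose ECG, on Day 4 before the continuous infusion ends.

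**The concern.** Leaving unscheduled values out of by-visit means is normal practice and is not at issue. The difficulty is with outputs whose purpose is to count subjects who crossed a limit. An unscheduled test or retest is often done because something looked abnormal, so it is a likely place to find the extreme value. A rule that picks the value nearest the target day takes no account of how extreme the others are.

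At stake is how a reader interprets a zero or a small number in a shift or QTcF table. It looks like a count of subjects who reached that level after dosing. As planned, it counts subjects whose selected value reached that level. This matters somewhat more because Protocol 11.2 names a laboratory threshold (serum creatinine above 2.0 mg/dL) as an event of special interest and asks the sponsor to assess how often such events occur, yet no SAP table counts such crossings at any time after dosing.

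**Working it through.** The plan gives no figure to reproduce, so the check sets the rules side by side, works one example and counts days.

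**1. Direction of the effect.** For one subject, let S be the set of selected values (at most one per analysis visit) and A the set of all post-dose values. S is contained in A. Hence, for any limit c, max(S) > c implies max(A) > c, but not the reverse. The number of subjects ever above c, based on S, is therefore less than or equal to the number based on A. The same holds for lower limits and for change from baseline. A single closed band, such as 450 to 480 msec, can move either way, because a subject may leave it for a higher band.

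**2. Example (values invented for illustration).** Appendix 1 gives the Day 4 ECG the window [3, 4]. Suppose QTcF is 510 ms on an unscheduled Day 3 ECG and 470 ms on Day 4. Day 4 is 0 days from target and Day 3 is 1 day from target, so 470 is kept. The Day 3 value is also excluded if the unscheduled-visit rule is applied.

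| QTcF row | Selected value (470) | Worst value (510) |
|---|---|---|
| above 500 | 0 | 1 |
| above 480, up to 500 | 0 | 0 |
| above 450, up to 480 | 1 | 0 |

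At the planned group sizes one subject is 1/120 = 0.8% (H and control) or 1/96 = 1.0% (L). In the curtailed sample one subject is a larger share.

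**3. Days outside any fixed window (Appendix 1, post-baseline).**

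- Covered: Days 1–11 (11), 14–15 (2), 20–24 (5) and 77–93 (17). Sum: 11 + 2 + 5 + 17 = 35 of 93 days.
- Not covered: 93 − 35 = 58 days, and 58/93 = 62% (Days 12–13, 16–19 and 25–76).

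A value from an uncovered day enters no by-visit table unless it falls in a discharge or discontinuation window. This is a share of calendar days, not of tests. How many tests fall on those days is not stated.

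**4. Where the unselected values go.** Section 6 puts them in the listings, and SAP section 13 orders listings by treatment first. Under Protocol 9.2.4.1 and 9.2.4.2, clinically significant laboratory and ECG abnormalities become adverse events, which are tabulated by group (Protocol 13.3.3; SAP Tables 14.3.1.1 to 14.3.1.3). What reaches no by-arm count is a crossing that was neither selected nor reported as an adverse event.

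**The case against.** The strongest reply is that nothing is hidden. Unscheduled and retest values are listed by treatment, SAP 7.3.2 adds a listing for subjects with clinically significant laboratory findings, and significant abnormalities at any visit are counted by arm as adverse events. By-time-point summaries are what Protocol 13.3.3 asks for, and they show minimum and maximum. The study ended early, its results are exploratory, and a limited sample can be read from listings. A worst-value count has its own bias, since more tests give more chances to cross a limit.

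Most of this stands and keeps the point small. It does not remove it. A listing is not a count, and SAP 14.1 names no laboratory listing (7.3.2 promises one, and section 14 calls its list a minimum). Adverse event status depends partly on judgement, and Protocol 9.2.4.2 does not require a separate event for an abnormal test whose symptom is already reported.

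Several stronger readings are tempting but unsupported:

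- That extreme values never appear by arm. Listings and adverse event tables can show them.
- That only scheduled visits are tabulated. Appendix 1 gives discontinuation assessments their own analysis visits.
- That an ECG on another day cannot enter the QTcF counts. A Day 3 ECG lies in the [3, 4] window and may be used if there is none on Day 4; for the change rows the text is simply open.
- That the undercount is greatest in a more toxic arm. This is plausible but rests on no figure in the documents.
- That vital signs are affected in the same way. No vital-sign threshold table is planned, so there is no such count to understate.

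**Conclusion.** The point holds in a limited form. No by-arm summary table captures the worst post-baseline laboratory or ECG value. Under the stated selection rules, the shift tables and the absolute QTcF rows can understate, and cannot overstate, the number of subjects who ever crossed a given limit. The time rule for the QTcF change rows is missing and should be stated.

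The size is unknown, as is any difference between arms. Both depend on how many unscheduled, retest and off-target values exist, which the documents do not give. The conclusion assumes that Table 14.3.4.2 follows the section 6 selection rule. Its title does not say so, but the time-point wording of the absolute categories points that way. Severity is low: the analysis is descriptive and exploratory, and the values remain available in listings.

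**What to change.** - Add a shift from baseline to worst post-baseline category to Tables 14.3.2.4 to 14.3.2.6, stating the direction that counts as worst for each parameter.
- Add an any-post-baseline row to Table 14.3.4.2 for every QTcF category, placing each subject in the absolute band of the highest value, and state the time rule for the 30 and 60 msec change rows.
- Base both on every post-dose value: scheduled, unscheduled, retest and discontinuation.
- Leave the by-visit summaries as planned.

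The cost is a few lines of SAP text and one derived record per subject and parameter, from data already collected. The downside is ascertainment: subjects tested more often have more chances to cross a limit. Show the number of tests per arm beside the counts. If the change is made after data lock, Protocol 13.4 requires the reason to be recorded and the result kept distinct from the planned analysis.
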